### 2.3.2. Pre-Clinical Pharmacology of Pembrolizumab

Therapeutic studies in mouse models have shown that administration of antibodies blocking PD-1/PD-L1 interactions enhance infiltration of tumor-specific CD8+ T cells and ultimately lead to tumor rejection, either as a monotherapy or in combination with other treatment modalities [Hirano, 2005; Blank, 2004; Weber, 2010; Strome, 2003; Spranger, 2014; Curran, 2010; Pilon-Thomas, 2010]. Anti-mouse PD-1 or anti-mouse PD-L1 antibodies have demonstrated antitumor responses in models of squamous cell carcinoma, pancreatic carcinoma, melanoma, acute myeloid leukemia and colorectal

carcinoma [Strome, 2003; Curran, 2010; Pilon-Thomas, 2010; Nomi, 2007; Zhang, 2004]. In such studies, tumor infiltration by CD8+ T cells and increased IFN- $\gamma$ , granzyme B and perforin expression were observed, indicating that the mechanism underlying the antitumor activity of PD-1 checkpoint inhibition involved local infiltration and activation of effector T cell function *in vivo* [Curran, 2010]. Experiments have confirmed the *in vivo* efficacy of anti-mouse PD-1 antibody as a monotherapy, as well as in combination with chemotherapy, in syngeneic mouse tumor models (see the Investigator's Brochure [IB], Keytruda IB, 2021).

### 2.3.3. Pembrolizumab Background

Pembrolizumab is a potent humanized immunoglobulin G4 (IgG4) monoclonal antibody (mAb) with high specificity of binding to the PD-1 receptor, thus inhibiting its interaction with PD-L1 and PD-L2. Based on preclinical *in vitro* data, pembrolizumab has high affinity and potent receptor blocking activity for PD-1. Pembrolizumab has an acceptable preclinical safety profile and is in clinical development as an intravenous (IV) immunotherapy for advanced malignancies. Keytruda (pembrolizumab) is indicated for the treatment of patients across a number of indications. For more details on specific indications refer to the Investigator brochure.

Keynote-183 was a randomized trial which evaluated pomalidomide and low-dose dexamethasone with or without pembrolizumab in subjects with relapsed and refractory multiple myeloma. The ORR was 34% in the pembrolizumab containing arm versus 40% in the control arm without pembrolizumab; however, there was no difference in time-to-progression between arms. There were 29 deaths in the pembrolizumab arm compared to 21 in the control arm, reflecting an overall survival hazard ratio of 1.61 (95% CI: 0.91, 2.85) [Krauss, 2018]. An analysis conducted with the removal of subjects with high-risk disease characteristics (high-risk cytogenetics, plasmacytoma and quadruple refractory status) resulted in a similar number of deaths (n=13) in both arms [Mateos, 2018].

Keynote-185 was a randomized trial which evaluated lenalidomide and dexamethasone with or without pembrolizumab in subjects with newly diagnosed multiple myeloma. The ORR was 64% in the pembrolizumab containing arm versus 62% in the control arm without pembrolizumab; however, there was no difference in time-to-progression between arms. There were 19 deaths in the pembrolizumab arm compared to 9 in the control arm, reflecting an overall survival hazard ratio of 2.06 (95% CI: 0.93, 4.55) [Krauss, 2018].

Refer to the Investigator's Brochure (IB)/approved labeling for detailed background information on MK-3475 [KEYTRUDA Product Information, 2018; Keytruda IB, 2021].

### 2.4. Assessment of Nonclinical Data for Belantamab Mafodotin when Co-Administered with Pembrolizumab

The current nonclinical and clinical safety information for both belantamab mafodotin and pembrolizumab, used as single agents, provide support for their use in combination in the target patient population. Based on the mechanism of action of belantamab mafodotin (following engagement with both target and the Fc $\gamma$ RIIIA, leading to ADCC

activity and the potential for cytokine release as a result of inflammation secondary to non-specific cytotoxicity) and the identified potential for pembrolizumab to cause cytokine release *in vitro*, there may be a potential risk for cytokine release when these agents are administered in combination. The risk is considered to be low. To ensure the safety of subjects, a careful dose escalation of belantamab mafodotin will be implemented where no more than one subject will be dosed per day.

In addition, the starting dose of belantamab mafodotin in this combination regimen has been selected to be 1 dose level below a dose that has been shown to be well tolerated during the belantamab mafodotin monotherapy dose escalation and should provide a sufficient safety margin when pembrolizumab is added at 200 mg. In addition, close clinical monitoring will be implemented.

### 3. OBJECTIVE(S) AND ENDPOINT(S)

#### Part 1: Dose Escalation

Objectives	Endpoints
Primary	

 
To determine safety, tolerability and to establish the RP2D of the combination of belantamab mafodotin with pembrolizumab in subjects with RRMM
 
	
 
Percent of subjects with AEs, changes in clinical signs and laboratory parameters
 
Number of subjects with dose limiting toxicities (DLTs)
 

Secondary	

 
To evaluate clinical activity of the combination of belantamab mafodotin and pembrolizumab in subjects with RRMM
 
	
 
Overall Response Rate (ORR), defined as the percentage of subjects with a confirmed partial response (PR) or better (i.e., PR, very good partial response [VGPR], complete response [CR] and stringent complete response [sCR]), according to the International Myeloma Working Group (IMWG) Response Criteria [Kumar, 2016].
 

 
To evaluate the pharmacokinetic profile of belantamab mafodotin when administered intravenously in combination with pembrolizumab
 
	
 
Pharmacokinetic parameters following IV administration as data permit.
 

 
To assess anti-drug antibodies (ADAs) against belantamab mafodotin
 
	
 
Incidence and titers of ADAs against belantamab mafodotin
 

Exploratory	

 
To assess Minimal Residual Disease (MRD) in subjects who achieve <math>\geq</math>VGPR or better
 
	
 
Minimal Residual Disease (MRD) negativity rate, defined as: the percentage of subjects who are MRD negative in subjects who achieve VGPR or CR
 

Objectives	Endpoints

 
To characterize the relationship between clinical response and other biologic characteristics
 
	
 
BCMA expression levels on malignant cells, serum sBCMA levels, serum cytokines, and immune cell characterization and their relationship to clinical response (Protein, RNA, DNA analysis)
 


 
To investigate the relationship between genetic variants in the host and response to belantamab mafodotin in combination with pembrolizumab
 
	
 
Possible relationship between host genetic variation and response to belantamab mafodotin in combination with pembrolizumab
 

 
To evaluate the tolerability of belantamab mafodotin in combination with pembrolizumab based on patient self-report of symptomatic adverse effects
 
	
 
Symptomatic adverse effects as measured by the Patient-reported outcome version of the Common Term Criteria for Adverse Events (PRO-CTCAE)
 
Impact of ocular adverse effects on quality of life as measured by the Visual Function questionnaire(s): National Eye Institute 25-item Visual Function Questionnaire (NEI-VFQ-25) and Ocular Surface Disease Index (OSDI)
 

 
To evaluate disease and treatment related symptoms and associated impacts on function and health-related quality of life
 
	
 
Exit Interview
 

- PK and ADA samples for pembrolizumab will be collected and stored during the trial. The analysis will be triggered only in case of unexpected clinical findings.

## Part 2: Expansion

Objectives	Endpoints
Primary	

 
To assess the clinical activity of the combination treatment with belantamab mafodotin and pembrolizumab in subjects with RRMM
 
	
 
Overall Response Rate (ORR), defined as the percentage of subjects with a confirmed PR or better (i.e., PR, VGPR, CR and sCR), according to the IMWG Response Criteria [Kumar, 2016].
 

Secondary	

 
To further evaluate the safety of belantamab mafodotin administered in combination with pembrolizumab in subjects with RRMM
 
	
 
Number (percent) of subjects with AEs, changes in clinical signs and laboratory parameters
 
Ocular finding on ophthalmic exam
 

 
To further assess the clinical activity of the combination treatment with belantamab mafodotin and pembrolizumab in subjects with RRMM
 
	
 
Clinical benefit rate (CBR), defined as the percentage of subjects with a confirmed minimal response (MR) or better per IMWG
 
Duration of response (DoR), defined as: the time from first documented evidence of PR or better, to the time when disease progression (PD) is documented per IMWG; or death due
 

Objectives	Endpoints
	
to PD occurs among subjects who achieve an overall response, i.e. confirmed PR or better
 
 
Time to response (TTR), defined as: the time between the date of first dose and the first documented evidence of response (PR or better) among subjects who achieved a confirmed response of PR or better
 
Time to best response, defined as the time between the date of first dose and the first best documented response (PR or better) among subjects who achieved a confirmed response of PR or better
 
Progression-free survival (PFS), defined as: the time from first dose until the earliest date of PD per IMWG, or death due to any cause
 
Time to disease progression (TTP), defined as: the time from first dose until the earliest date of PD per IMWG, or death due to PD
 
Overall Survival (OS), defined as the time from first dose until death due to any cause
 


 
To evaluate the pharmacokinetic profile of belantamab mafodotin when administered intravenously in combination with pembrolizumab
 
	
 
Pharmacokinetic parameters following IV administration as data permit.
 

 
To assess ADAs against belantamab mafodotin
 
	
 
Incidence and titer of ADA to belantamab mafodotin
 

Exploratory	

 
To assess Minimal Residual Disease (MRD) in subjects who achieve <math>\geq</math>VGPR or better
 
	
 
Minimal Residual Disease (MRD) negativity rate, defined as: the percentage of subjects who are MRD negative in subjects who achieve VGPR or CR
 

 
To characterize the relationship between clinical response and other biologic characteristics
 
	
 
BCMA expression levels on malignant cells, serum sBCMA levels, serum cytokines, and immune cell characterization and their relationship to clinical response (Protein, RNA, DNA analysis).
 

 
To investigate the relationship between genetic variants in the host and response to belantamab mafodotin in combination with pembrolizumab
 
	
 
Possible relationship between host genetic variation and response to belantamab mafodotin administered in combination with pembrolizumab
 

 
To explore the effect of belantamab mafodotin in combination with pembrolizumab on symptoms and health-related quality of life in subjects with RRMM
 
	
 
Changes from baseline in symptoms and health-related quality of life as measured by the European Organisation for Research and Treatment of Cancer Quality of Life
 

Objectives	Endpoints
	Questionnaire 30-item Core Module (EORTC-QLQ-C30) and European Organisation for Research and Treatment of Cancer Quality of Life Questionnaire 20-item Multiple Myeloma Module (EORTC-QLQ-MY20)

 
To evaluate the tolerability of belantamab mafodotin in combination with pembrolizumab based on patient self-report of symptomatic adverse effects
 
	
 
Symptomatic adverse effects as measured by the PRO-CTCAE
 
Impact of ocular adverse effects on quality of life as measured by the Visual Function questionnaire(s): NEI-VFQ-25 and OSDI
 

 
To evaluate disease and treatment related symptoms and associated impacts on function and health-related quality of life
 
	
 
Exit Interview
 

- PK and ADA samples for pembrolizumab will be collected and stored during the trial. The analysis will be triggered if unexpected clinical findings have been identified.

## 4. STUDY DESIGN

### 4.1. Overall Design

This is a phase I/II, single arm, open label, two-part study to determine the RP2D of belantamab mafodotin administered in combination with 200 mg of pembrolizumab, and to evaluate safety and clinical activity of the combination in subjects with RRMM. The study will be conducted in two parts: Part 1: dose escalation of belantamab mafodotin with a constant dose of pembrolizumab at 200 mg, and Part 2: expansion cohort at RP2D of belantamab mafodotin in combination with 200 mg pembrolizumab. A total of up to 40 evaluable subjects with RRMM will be enrolled into this study (up to 12 in Part 1, and 28 in Part 2).

[figure not shown]
### 4.2. Study Treatment and Duration

#### 4.2.1. Study Treatment

The treatment schematic is depicted in [Figure 1](#).

This is a single arm, open label study. Subjects in Part 1 and in Part 2 will receive belantamab mafodotin and pembrolizumab via IV infusion on day 1 of each 21-day cycle. Belantamab mafodotin will be administered first, as an IV infusion, followed by at least 1 hour rest. Refer to the SRM for details on belantamab mafodotin infusion. Provided there is no infusion related reaction (IRR) warranting a prolonged interval between dosing, pembrolizumab will be administered as second drug over approximately 30 min via IV infusion. If a subject develops IRR during or after belantamab mafodotin infusion, he or she will be treated according to institutional guidelines. In such cases the infusion of pembrolizumab may have to be delayed until IRR has recovered to Grade 1 or less, and investigator considers it safe to continue with infusion with pembrolizumab. The infusion of pembrolizumab may be delayed for up to the +3 day window from scheduled visit to allow for recovery of IRR, and to accommodate scheduling conflicts. If a subject does not recover from IRR to Grade 1 or less within the +3 day window, the dosing of pembrolizumab will be skipped in a given cycle, and may be resumed in the next cycle.

**Figure 1** Study Treatment Schematic

**Dosing:**

- Belantamab mafodotin and pembrolizumab on D1 of each cycle
- Belantamab mafodotin first, Pembrolizumab as second iv infusion (1hr apart)
- If IRR related to GSK2857916, the D1 dosing will be delayed
- Max treatment duration: 35 cycles combination treatment

#### 4.2.2. Duration of Treatment

[figure not shown]
Subjects will be treated until disease progression, intolerable toxicity, informed consent withdrawal, or for a maximum of 35 cycles (approximately 2 years).

After the study treatment discontinuation, subjects will undergo end of treatment assessments 30 days ( $\pm 7$  days) after the last dosing, or prior to the start of new anti-cancer treatment (whichever occurs first). Subjects who discontinued treatment for reasons other than PD, will be followed up every 3 weeks until confirmed PD, initiation of a new anticancer therapy or death. All subjects with confirmed PD will be followed for OS and subsequent anti-cancer therapy every 3 months until the end of study. End of study is defined in Section [5.5.2](#).

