Hepatotoxicity	
Belantamab mafodotin: In nonclinical studies liver is a target organ for toxicity, with increased liver weights and/or raised hepatobiliary enzymes and transaminases observed in both rat and monkey. These changes in the liver were without clinical consequence in the shorter duration studies and in the rat 13-week study. In the monkey 13-week study, progression of liver toxicity to include minimal multifocal hepatocellular necrosis was observed at all doses administered (<math>\geq 3</math> mg/kg/week).
 
Mild elevations of liver enzymes have been reported in some patients treated with belantamab mafodotin.
 
Pembrolizumab: Hepatitis has been reported with pembrolizumab treatment.
	
Only subjects with well-preserved liver function per the inclusion/exclusion criteria will be allowed on study.
 
Subjects with Hepatitis B (HBV) and C will be excluded.
 
Liver function tests will be frequently monitored. In case of liver abnormalities, management will be implemented according to clinical practice. Subjects that meet liver stopping criteria (Section 5.4.1.1) will be withdrawn from the study.

Nephrotoxicity	
Belantamab mafodotin: Non-clinical safety studies have demonstrated dose dependent and reversible primary glomerular injury and tubular degeneration (in rat and monkey), accompanied by large molecular proteinuria (albuminuria) and enzymuria. Single cell necrosis of the kidney and bladder urothelium was also noted in the 13-week monkey study. Severe tubular degeneration/regeneration and marked glomerulonephritis exacerbated by immune complex disease, likely
	
Subjects will be monitored for kidney function by assessing creatinine, eGFR, electrolytes, and albumin/creatinine ratios (spot urine).
 
Subjects will be educated about the need of maintaining adequate urinary output.

Potential Risk of Clinical Significance	Summary of Data/Rationale for Risk	Mitigation Strategy

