#### 5.4.1.2. Study Treatment Restart or Rechallenge

If subject meets liver chemistry stopping criteria do not restart/rechallenge subject with study treatment unless:

- GSK Medical Governance approval is granted (as described below),
- Ethics and/or IRB approval is obtained, if required, and
- Separate consent for treatment restart/rechallenge is signed by the subject

If GSK Medical Governance approval to restart/rechallenge subject with study treatment is not granted, then subject must permanently discontinue study treatment and may continue in the study for protocol-specified follow up assessments.

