##### Symptomatic subject:

Obtain cardiology consultation immediately. Permanently discontinue belantamab mafodotin and withdraw the subject from the study.

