#### **5.4.1.8. Infusion-Related Reactions**

##### ***Infusion-Related Reactions Associated with Belantamab Mafodotin***

Premedication is not required prior to infusion of belantamab mafodotin unless deemed medically appropriate by the investigator following evaluation of infusion related reactions. Premedication should be considered in any subject who experienced an infusion related reaction at first or any subsequent infusion with belantamab mafodotin.

Infusion-related reactions should be managed by guidelines provided in [Table 4](#). A subject that experiences a Grade 4 IRR after belantamab mafodotin, should be permanently withdrawn from the study.

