**5.4.1.9. Allergic and Anaphylactic reaction stopping criteria**

All subjects will be monitored carefully for evidence of allergic response. A subject that exhibits signs or symptoms of severe hypersensitivity or anaphylaxis will receive appropriate medical treatment and be permanently withdrawn from the study.

Additional stopping criteria in case of significant toxicity are provided in Section [6.5.1](#)

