Spot Urine (albumin / creatinine ratio) 	X			
 
1. All assessments will apply to Part 1 and 2 unless stated otherwise.
 
2. Safety follow up to occur within 30 days from the last dose, or prior to the new anti-MM treatment (whichever occurs first).
 
3. PFS follow-up every 21 days (<math>\pm 7</math> days) for subjects who discontinue IP for a reason other than PD. Disease evaluations will continue until confirmed PD, death, start of a new anticancer treatment, withdrawal of consent, or end of the study whichever occurs first. Once subject progresses, move to OS Follow-up.
 
4. The survival for MM will be documented in medical charts. No visit necessary. Contacts will be made via phone calls, emails or other means of communications every 12 weeks (<math>\pm 14</math> days) until end of study (Section 5.5.2). Subject does not need to come in for visit unless they are being followed for corneal signs that are present at the end of study treatment.
 
5. AE/SAEs will be collected to 45 days post the last dose. All related SAEs are to be collected from first dose through OS follow-up. AEs/SAEs will be followed until the event is resolved, stabilized, otherwise explained or subject is lost to follow up.
 
6. If a subject develops signs / symptoms, or they require additional treatment, e.g. topical steroid for more than 7 days, additional assessment by an ophthalmologist (or optometrist, if ophthalmologist is not available) will be implemented. Intraocular pressure should be monitored if steroid eye drops are used more than 7 days. See Section 7.3.5 for list of exams.
 
7. Subjects with decreased visual acuity or corneal signs or symptoms at the end of study treatment visit will have follow-up ophthalmic exams at 3 and 6 weeks from the last dose of study treatment and then every 6 weeks (<math>\pm 7</math> days) until deemed clinically stable by an eye care professional, or up until 1 year (whichever comes first). See Section 7.3.5 for list of exams.
 
8. Perform only in women of child-bearing potential. May be either serum or urine.
 
9. Final pregnancy test (serum or urine) must be performed in women of childbearing potential at the EOT Visit. Follow up pregnancy assessment by telephone (for WOCBP only) should be performed 4 months after the last dose of belantamab mafodotin.
 
10. eGFR as calculated by Modified Diet in Renal Disease (MDRD) formula (Appendix 3)
 
11. Albumin / creatinine ratios (spot urine from first void).
 

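### Only subjects with confirmed PD are routed into OS follow-up, and several toxicity rules say withdrawal from the study, so OS may be incomplete and informatively censored

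*Protocol*

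**What the plan says.** **Who is followed for survival.** Under Section 4.2.2, subjects who stop treatment for reasons other than PD "will be followed up every 3 weeks until confirmed PD, initiation of a new anticancer therapy or death". The next sentence is the only route onward: "All subjects with confirmed PD will be followed for OS and subsequent anti-cancer therapy every 3 months until the end of study". Section 5.4 and the synopsis repeat both rules in substance. Table 10 note 3 also ends disease evaluation at the start of a new anticancer treatment, and its only onward instruction is "Once subject progresses, move to OS Follow-up". The synopsis restricts collection of the next therapy to subjects whose PD was confirmed before that therapy began.

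**Toxicity exits.**
- Section 5.4.1.5, for a symptomatic subject with raised troponin: "Permanently discontinue belantamab mafodotin and withdraw the subject from the study". The same instruction is given for an asymptomatic subject whose repeat value passes the local threshold for infarction.
- Section 5.4.1.8: a subject with a Grade 4 reaction to belantamab mafodotin "should be permanently withdrawn from the study".
- Section 5.4.1.9: a subject with severe hypersensitivity or anaphylaxis is to "receive appropriate medical treatment and be permanently withdrawn from the study".
- Table 2, hepatotoxicity: subjects meeting the liver stopping criteria "will be withdrawn from the study".

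Section 5.4, by contrast, lists the safety stopping criteria among reasons to discontinue treatment and then puts non-PD discontinuations into 3-weekly follow-up. Section 5.4.1.2 says that a subject who met the liver criteria and is not approved for restart stops treatment but "may continue in the study for protocol-specified follow up assessments".

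**Analysis.** Table 15 defines OS as first dose to death from any cause. It censors at withdrawal of consent or loss to follow-up, or at the last known alive or last contact date if the subject is alive at cut-off. Section 9.8 includes data up to completion of, or withdrawal from, the study.

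**The concern.** An endpoint that counts every death needs vital status on every treated subject. The schedule supplies it only to subjects who progress first. The others stop for toxicity, by choice or after 35 cycles, and then move to another therapy without confirmed PD. They are censored at their last contact, and a later death can go unrecorded. Subjects withdrawn from the study for toxicity are affected in the same way if sites take those sections literally.

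Neither exit is random. A toxicity or a decision to change therapy plausibly carries prognostic information, so the Kaplan-Meier assumption that leavers resemble those who remain is doubtful. With at most 40 subjects (28 in Part 2), each lost subject is 1/40 = 2.5% to 1/28 = 3.6% of the OS analysis. No analysis plan can recover vital status that was never collected. For the toxicity exits, sites also hold two instructions that cannot both be followed.

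**Working it through.** **1. Text check: new therapy before PD.**

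| Place | Follow-up of non-PD discontinuation ends at | Entry to OS follow-up |
|---|---|---|
| Synopsis | confirmed PD, new therapy, death | confirmed PD |
| Section 4.2.2 | confirmed PD, new therapy, death | confirmed PD |
| Section 5.4 | confirmed PD, new therapy, death | confirmed PD |
| Table 10 note 3 | confirmed PD, death, new therapy, consent withdrawal, end of study | progression |
| Table 10 note 4 | not addressed | not addressed; gives method and 12-week interval of contact |
| Section 5.5.1 | not addressed | not addressed; completion means followed to death or end of study |

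No row gives an entry route to a subject who starts new therapy without confirmed PD.

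**2. Text check: toxicity exits.**

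| Event | Leaves the study | Stops treatment, follow-up continues |
|---|---|---|
| Troponin (symptomatic, or above infarction threshold) | 5.4.1.5 | 5.4 (general rule) |
| Grade 4 infusion reaction | 5.4.1.8 | 5.4 (general rule); Table 4 says only to discontinue permanently |
| Severe hypersensitivity or anaphylaxis | 5.4.1.9 | 5.4 (general rule) |
| Liver stopping criteria | Table 2 | 5.4.1.2, same criteria |

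For liver the conflict is direct. For the others it is between a specific section and the general rule. The LVEF and valve rules (5.4.1.4, 5.4.1.6) stop treatment and continue monitoring, so the document does make the distinction elsewhere.

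**3. Size (illustration).** The protocol states no OS figure to reproduce. Inputs:
- Median OS while in follow-up: 12 months or 9 months, the ends of the historical range in Section 2.1.
- *f*, the share leaving follow-up by month 12 if nobody died: 10%, 20%, 30%. **Assumption.**
- *m*, hazard after leaving divided by hazard before: 0.5 to 3. **Assumption.**
- Constant hazards. **Assumption.**

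Let h = ln 2 / median and λ = −ln(1 − f)/12. Kaplan-Meier censored at exit estimates e^(−12h). With everyone followed, survival at t = 12 is

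S = A + λ(B − A)/(h + λ − mh), where A = e^(−12(h+λ)) and B = e^(−12mh).

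Example with median 12, f = 20%, m = 2: h = 0.05776, λ = 0.01860, A = 0.5 × 0.8 = 0.400, B = 0.5² = 0.250. So S = 0.400 + 0.01860 × (−0.150)/(−0.03917) = 0.400 + 0.071 = 0.471. The censored estimate is 0.500, so the overstatement is 2.9 points.

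12-month OS with full follow-up, median 12 (the censored estimate is 50.0% throughout):

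| f | m = 0.5 | m = 1 | m = 1.5 | m = 2 | m = 3 |
|---|---|---|---|---|---|
| 10% | 51.0 | 50.0 | 49.2 | 48.6 | 47.7 |
| 20% | 52.0 | 50.0 | 48.4 | 47.1 | 45.3 |
| 30% | 53.1 | 50.0 | 47.5 | 45.6 | 42.8 |

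For m = 1.5 to 3 the overstatement runs from 50.0 − 49.2 = 0.8 to 50.0 − 42.8 = 7.2 points. With median 9 (censored estimate 39.7%), full follow-up gives 38.9% at f = 10%, m = 1.5 and 32.9% at f = 30%, m = 3, so 0.8 to 6.8 points. At m = 0.5 OS is understated by 1.0 to 3.1 points (median 12).

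Deaths pre-empt some exits, so the share actually leaving alive by month 12 is below f: λ/(h + λ) × (1 − A) = 0.2435 × 0.600 = 14.6% in the example.

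**4. Primary endpoint.** N = 28 comes from the response-rate hypotheses (Sections 9.1.2 and 9.2.2). Survival follow-up does not enter it.

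**The case against.** The best defence is that the protocol's intent is broader than Section 4.2.2. Section 5.5.1 expects follow-up to death or end of study, with the eCRF completed every 3 months. Table 10 note 4 describes survival contacts without mentioning PD. Table 15 has no censoring category for new therapy. This shows that the intent was probably full follow-up, but a general aim and a contact method do not tell a site which subjects to call, and the four places that do so all name progression.

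The defence also says that the withdrawal phrases are loose wording for stopping treatment. That may be so for troponin, infusion reactions and anaphylaxis, but Table 2 and Section 5.4.1.2 cannot both hold for liver, and Section 9.8 makes study withdrawal matter for the data.

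Stronger readings are tempting, but the documents do not support them:
- *That these subjects are not observed at all after new therapy.* Section 7.3.1.1 collects AEs to 45 days after treatment regardless of new therapy, all SAEs to 45 days, and related SAEs up to any follow-up contact. Table 10 note 7 continues eye examinations for up to a year in affected subjects. The gap is in survival status beyond that.
- *That PFS is equally flawed.* Ending disease assessment at new therapy is a common convention, and Table 15 leaves PFS censoring dates to the RAP.
- *That OS is certainly overstated.* The direction depends on the post-exit hazard, which the protocol does not give.
- *That the excess deaths in KEYNOTE-183 and KEYNOTE-185 carry over.* Those arose with an immunomodulatory agent plus dexamethasone (Section 2.3.3). They are a reason to want complete vital status, not evidence about this combination.

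Finally, sampling error is larger than the bias: the 95% half-width of a 50% estimate with complete follow-up is 1.96 × √(0.25/28) = 18.5 points, or 15.5 points with 40 subjects. That tempers the importance; it does not justify an avoidable systematic error.

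**Conclusion.** The point holds as a gap and a contradiction in follow-up. As written, a subject who starts new therapy before confirmed PD has no scheduled survival contact, and four toxicity rules conflict with the general instruction to keep following such subjects, directly so for liver. OS may therefore be informatively censored. The size is an illustration resting on assumed exit shares, post-exit hazard ratios and constant hazards: about 1 to 7 points of overstatement at 12 months for 10% to 30% leaving and hazard ratios of 1.5 to 3, none at 1, and a reversed bias at 0.5. Neither direction nor size can be fixed from the protocol. OS is a secondary, descriptive endpoint in a single-arm study; the ORR test, its error rates and N = 28 do not change. It should still be corrected in the protocol, because the missing data cannot be recovered at analysis.

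**What to change.** 1. In Sections 4.2.2 and 5.4, the synopsis and Table 10 note 3, state that every treated subject who ends treatment or PFS follow-up for any reason other than death or withdrawal of consent, including start of new therapy before PD, enters OS and subsequent-therapy follow-up every 12 weeks until end of study. Remove the synopsis limit on collecting next therapy to PD-first subjects.
2. Reconcile the study-withdrawal wording in Sections 5.4.1.5, 5.4.1.8, 5.4.1.9 and Table 2 (liver) with Sections 5.4 and 5.4.1.2, so that stopping study treatment is separate from leaving survival and safety follow-up. Keep each section's treatment-stopping effect unchanged. In 5.4.1.8 (Grade 4 reaction) and 5.4.1.9 the withdrawal phrase is the only stop instruction given there, so it must not be deleted without the treatment stop being stated in its place.

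The cost is amendment wording plus a small number of 12-weekly remote contacts, for which Table 10 note 4 already describes the method. No sample size or ORR analysis changes.
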